In cases where there are no sufficient recordings of clinical stability as defined above, the endpoint will be censored. Censoring will be at the first time of clinical stability, if and only if after this observation there is no recording of non-resolved influenza symptoms (ignoring missing recordings). If there are no recordings of resolved symptoms satisfying this criterion, the time of censoring is the first possible time point an assessment could have been done after the last observation of vital signs recordings, which is 13:00 on the same day if the last observation was a morning assessment (from 3:01 until 11:00), 21:00 if the last observation was an afternoon assessment (from 11:01 until 19:00), 5:00 the next day if the last assessment was an evening assessment (from 19:01 until 03:00). There are two exceptions: in case the last available vital signs record is on the day of discharge in the evening or on day 14 during hospitalization in the evening. If at this record (last record for the subject to be taken into account for time to clinical stability) there is no clinical stability, the time of the last assessment (day of discharge, evening or day 14, evening) will be taken as the time of censoring.

The data will be presented using a Kaplan-Meier curve and Kaplan-Meier estimates by treatment group, overall and by age group. The time to event data will be modeled using the accelerated failure time model. The model will use the parametric shape, selected based on the goodness of fit criterion (AIC), and may take a Weibull, log-logistic, lognormal, or gamma distribution. Age category, NEW Score at baseline and treatment group will be included as covariates. If the data don't provide an acceptable model fit, alternatively a Cox proportional hazards model can be used (in case the hazards are proportional). In case a Cox proportional hazards model is used a Log-log plot of survival will be added to check the proportional hazard assumption. Additionally, the time to event data will be analyzed using the logrank test and the Gehan-Wilcoxon method.

Table 6: Resolution Criteria for Vital Signs

Assessment	Resolution Criterion
Temperature	Oral temperature ≤ 36.5 °C for elderly and ≤ 37.2 °C for adults
Oxygen saturation	$\geq 92\%$ on room air without supplemental oxygen*
Respiration rate	≤ 24 /min
Heart rate	≤ 100 /min
Systolic blood pressure	≥ 90 mmHg

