*On room air to be obtained from “Was oxygen saturation measured on room air?” on Vital Signs pages (SUPPVS.QVAL for SUPPVS.QNAM = ‘VSOXSMRA’)

▪ **Time to improvement of respiratory status**

Time to improvement of respiratory status is defined as the time (in hours) from first study treatment until the first assessment (actual date and time) of a successive series of 3 recordings (over 4 scheduled successive analysis time points, 1 missing time point is allowed) where normalization of blood oxygen saturation and respiration rate occurred (as defined in Table 6). Analysis performed will be analogous to the analysis for the time to improvement of vital signs. Note that the NEW Score at baseline should not be added as covariate in the models.

▪ **Clinical outcome on day 8**

The ordinal scale consists of 6 categories that are exhaustive, mutually exclusive, and ordered (Table 7). For all patients, the category at days 1 to 15 will be established as the worst category on that day. The clinical outcome on day 8 will be further analyzed.

The analysis of the clinical outcome on day 8 will be performed using a proportional odds model, modeling the common odds ratio of the improvement on the ordinal scale of active treatment versus control. Age category (≥ 18 - < 65 years, ≥ 65 - ≤ 85 years) and baseline clinical outcome category will be added to the model. In case the model will not fit, age category and subsequently baseline category will be deleted.

In case of missing data ($>10\%$), multiple imputation under the missing-at-random assumption will be employed as a sensitivity analysis. The Markov chain Monte Carlo (MCMC) method will be used to create a number of multiple imputation datasets with monotone missingness in the clinical outcomes (baseline until day 15). The number of imputation datasets will be the same as the percentage of missing data (White *et al.* 2011). A monotone ordinal logistic regression imputation model will be used to complete the remaining missing clinical outcomes. The models fitted using the multiple imputation datasets will be the same as the final model on the actual data. The results from the models on the multiple imputation datasets will be combined taking into account the between and within variation of the results.

Additionally a Wilcoxon–Mann–Whitney test will be performed to compare the clinical outcome on day 8 between the two treatments.

Table 7: Ordinal scale on Day 8

Outcome
Death

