The time to return to usual activity and the time to return to usual health are defined as the time in hours from the first dose of investigational product till the first one of 2 successive cases where the response is 'Yes' on respectively FLU-PRO additional question 7 and FLU-PRO additional question 9. Missing data within the series are allowed as long as within three successive planned recordings there is at most 1 recording missing.

In cases where there are no sufficient recordings of return to usual activity/health as defined above, the endpoint will be censored. Censoring will be at the first time of return to usual activity/health, if and only if after this observation there is no recording of difficulties in usual activities/health (ignoring missing recordings). If there are no recordings of return to usual

activity/health satisfying this criterion, the time of censoring is the time of the last diary entry + 24 hours. One exception is censoring at the Day 28 Visit (last study day for the subject). If the subject is not returned to usual activity/health on this day, the time of the last diary entry will be taken as the time of censoring.

Data will be presented using Kaplan-Meier curves and Kaplan-Meier estimates by treatment group, overall and by age group. For a comparison between treatment arms, the time to parameters will be analyzed using an accelerated failure time model. The model will use the parametric shape, selected based on the goodness of fit criterion (AIC), and may take a Weibull, log-logistic, lognormal, or gamma distribution. As baseline covariates the ordinal scale at baseline category (ICU, ward+O₂, ward-O₂) and the age category (≥ 18 - < 65 years, ≥ 65 - ≤ 85 years) will be included. If the data don't provide an acceptable model fit, alternatively a Cox proportional hazards model can be used (in case the hazards are proportional). In case a Cox proportional hazards model is used a Log-log plot of survival will be added to check the proportional hazard assumption. Additionally, the time to event data will be analyzed using the logrank test and Gehan-Wilcoxon method.

- **Time to significant reduction in influenza symptom severity.**

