The time to significant reduction in influenza symptom severity (to mild or none for all influenza symptoms) is defined as time in hours from the first dose of investigational product until the first of 2 successive recordings in which the total score for each of the 2 recordings are lower or equal to 1 and all the domain scores are lower or equal to 1. The 2 successive recordings should have been done within 3 scheduled successive analysis timepoints (one missing in between is allowed).

Censoring will be done similar to the FLU-PRO time to return to usual activity and time to return to usual health as specified above.

Data will be presented using Kaplan-Meier curves and Kaplan-Meier estimates. For a comparison between treatment arms, the time to significant reduction in influenza symptom severity will be analyzed using an accelerated failure time model. The model will use the parametric shape, selected based on the goodness of fit criterion (AIC), and may take a Weibull, log-logistic, lognormal, or gamma distribution. As baseline covariate the age category (≥ 18 - < 65 years, ≥ 65 - ≤ 85 years) and baseline FLU-PRO total score will be included. If the data don't provide an acceptable model fit, alternatively a Cox proportional hazards model can be used (in case the hazards are proportional). In case a Cox proportional hazards model is used a Log-log plot of survival will be added to check the proportional hazard assumption. Additionally, the time to event data will be analyzed using the logrank test and Gehan-Wilcoxon method.

- **Proportion of patients with a significant reduction in influenza symptom severity.**

The proportion of subjects with a significant reduction in symptom severity (the total score for each of the 2 recordings are lower or equal to 1 and all the domain scores are lower or equal to 1) at each assessment will be tabulated.

4.2.7. *FLU-iiQTM Additional Daily Diary Items*

For the 9 additional daily diary items of FLU-PRO frequency distributions of the number (%) of subjects per additional FLU-PRO item and per response category will be shown at baseline and all post-baseline assessments, per treatment group.

4.2.8. *Correlation between viral load, viral titer and changes in clinical symptoms*

- **Correlation between the decline in viral load, the decline in viral titer and clinical symptoms**

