The time to influenza A viral negativity (see definition in section 4.2.2) measured by viral load and viral titer will be correlated with the following clinical measures (see definitions in sections 4.2.3 and 4.2.6):

1. Time to resolution of symptoms (7 primary symptoms)
2. Time to resolution of symptoms (All symptoms)
3. Time to return to usual activity,
4. Time to return to usual health and
5. Time to significant reduction in influenza symptom severity

Scatter plots with smoother curve will be shown per treatment group for the above mentioned correlations. An additional table will be provided showing the spearman correlation coefficients.

- **Correlation between the viral load, viral titer and severity of clinical symptoms**

The post-baseline log₁₀ values of viral load and post-baseline log₁₀ values of viral titer from day 2 to day 7 will be correlated with the following severity of clinical symptoms (see definitions in sections 4.2.3 and 4.2.6):

1. Flu-iiQTM daily average symptom score post-baseline from day 2 to day 7
2. FLU-PRO total score post-baseline from day 2 to day 7

Scatter plots with smoother curve will be shown per treatment group for the above mentioned correlations. An additional table will be provided showing the spearman correlation coefficients.

- **Correlation between baseline viral load, baseline viral titer and clinical symptoms**

The baseline viral load and baseline viral titer will be correlated with the following clinical measures (see definitions in sections 4.2.3 and 4.2.6):

1. Time to resolution of symptoms (7 primary symptoms)
2. Time to resolution of symptoms (All symptoms)
3. Time to return to usual activity,
4. Time to return to usual health and
5. Time to significant reduction in influenza symptom severity

Scatter plots with smoother curve will be shown per treatment group for the above mentioned correlations. An additional table will be provided showing the spearman correlation coefficients.

4.2.9. *Other Outcomes*

▪ **Time to hospital discharge**

The time to hospital discharge will be calculated from the date of first study drug intake during hospitalization up to the date of discharge. Subjects still hospitalized at the end of the study (end date of hospitalization missing or after trial termination) will be censored at the trial termination date.

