Data will be presented using Kaplan-Meier curves and Kaplan-Meier estimates. For a comparison between treatment arms, the time to hospital discharge in days will be analyzed using an accelerated failure time model. The model will use the parametric shape, selected based on the goodness of fit criterion (AIC), and may take a Weibull, log-logistic, lognormal, or gamma distribution. As baseline covariate the age category (≥ 18 - < 65 years, ≥ 65 - ≤ 85 years) will be included. If the data don't provide an acceptable model fit, alternatively a Cox proportional hazards model can be used (in case the hazards are proportional). In case a Cox proportional hazards model is used a Log-log plot of survival will be added to check the proportional hazard assumption. Additionally, the time to event data will be analyzed using the logrank test and the Gehan-Wilcoxon method.

4.3. **Safety**

All safety analyses will be done on the Safety Set. Analyses will be presented overall and by age category and by treatment group.

4.3.1. *Adverse events*

Pre-treatment AEs are defined as AEs that were reported or worsened after signing the ICF up to the start of study drug dosing. Treatment-emergent AEs (TEAE) are defined as AEs that were reported or worsened on or after the start of study drug dosing through the 28-day Safety Follow-up Visit.

Adverse events with a start date and time recorded will be allocated based on their start date and time. If there is no time recorded for the start of the adverse event the adverse event that occurred on or after the day of first treatment intake and not after the 28-day safety follow up visit will be considered as treatment-emergent. Only adverse events that occur before the day of first medication intake and after/on the day of signing ICF will be considered as pre-treatment.

In case the start date of an adverse event is partially or completely missing, a worst case allocation will be done using the available date and time information in the start and end date time of the adverse event (i.e. if possible based on the available information the adverse event will be allocated to the treatment phase and hospitalization sub period).

Adverse events

The variables related with adverse events are

- AE term (verbatim and MedDRA preferred term and system organ class)
- Onset date, End date and duration of AE
- Serious AE (Yes/No)
- Severity (Mild, Moderate, Severe, Life threatening)

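### Time to hospital discharge and time to respiratory improvement adjust for age category but not for baseline severity, which the SAP already derives and uses in other models; precision may be lost

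*SAP*

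**What the plan says.** **Discharge (SAP 4.2.9).** The AFT model compares the arms with one baseline covariate: "As baseline covariate the age category". A Cox model is the fallback, with logrank and Gehan-Wilcoxon analyses in addition. Time is "calculated from the date of first study drug intake during hospitalization up to the date of discharge", in days, with no formula.

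**Respiratory improvement (SAP 4.2.1).** "Analysis performed will be analogous to the analysis for the time to improvement of vital signs". The vital-signs model reads "Age category, NEW Score at baseline and treatment group will be included as covariates". For the respiratory endpoint the SAP then adds: "Note that the NEW Score at baseline should not be added as covariate in the models". Age category and treatment remain. The SAP gives no reason and names no replacement.

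**Other models.**
- Day 8 ordinal outcome (SAP 4.2.1): besides age category, "baseline clinical outcome category will be added to the model".
- Return to usual activity or health (SAP 4.2.6): "As baseline covariates the ordinal scale at baseline category" (ICU, ward with oxygen, ward without oxygen), plus age category.
- Symptom reduction (SAP 4.2.6): "baseline FLU-PRO total score will be included", with age category.
- Viral negativity (SAP 4.2.2), symptom resolution (4.2.3) and resumption of normal activities (4.2.4): baseline viral load, symptom score or impact score, with age category.

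**Design.** Allocation is 2:1, stratified by age cohort only (SAP 1.5). Enrollment is up to 90, with at least 60 thought feasible (SAP 1.4). No formal hypothesis testing is planned for efficacy (SAP 4.2). Protocol 11.6 names no covariates for discharge.

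**The concern.** Every other AFT model in the SAP carries a baseline severity measure or the baseline value of the outcome. These two are the exceptions, although a suitable covariate is already derived. Severity is not balanced by design, and the placebo arm will have 20 to 30 subjects. If severity at entry predicts length of stay or respiratory recovery beyond age, the planned models give wider intervals than the data allow and leave a chance imbalance in the treatment estimate. A covariate added after unblinding would carry little weight, so the choice has to be made in advance.

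A smaller matter concerns discharge only. Read as a plain difference of dates, a discharge on the date of first intake gives time 0, whose logarithm is undefined, so the AFT fit would lose that subject.

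**Working it through.** **Plan's own figure.** The documents give no event count, power or precision for either endpoint, so there is nothing to reproduce. The precision figures in SAP 1.4 concern pharmacokinetics and adverse events.

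**Inputs**
- Arm sizes 60:30 (maximum) and 40:20 (at the feasible 60): SAP 1.4 and 1.5.
- R²: share of residual log-time variance explained by baseline severity beyond age and treatment. Not in the documents; assumed at 0, 0.10, 0.20 and 0.30.
- SD of log time: assumed 0.7, used only to put the intervals on the time-ratio scale.

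**Formulas (lognormal AFT)**
- CI width on the log scale relative to age-only adjustment = √(1 − R²).
- Equivalent sample size = 1/(1 − R²).
- Cost of one extra parameter at R² = 0 = √((n − 4)/(n − 5)): √(56/55) = 1.009 at n = 60, √(86/85) = 1.006 at n = 90.
- 95% CI factor on the time ratio = exp(1.96 × 0.7 × √(1/n₁ + 1/n₂) × √(1 − R²)). At R² = 0 this is exp(1.96 × 0.7 × 0.2236) = 1.36 for 60:30 and exp(1.96 × 0.7 × 0.2739) = 1.46 for 40:20.

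| R² (assumed) | Relative CI width | Equivalent N for 90 | CI factor 60:30 | CI factor 40:20 |
|---|---|---|---|---|
| 0 | about 1.01 | about 90 | 1.36 | 1.46 |
| 0.10 | 0.949 | 100.0 | 1.34 | 1.43 |
| 0.20 | 0.894 | 112.5 | 1.32 | 1.40 |
| 0.30 | 0.837 | 128.6 | 1.29 | 1.37 |

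Apart from the 1.01 in the first row, the table ignores the cost of the extra parameters.

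**Simulation check.** 600 trials per scenario, 40:20, a three-level severity factor (45%, 45%, 10%), log-SD 0.7, time ratio 0.75 and follow-up cut at 28 days, all assumed. Least squares on log time stood in for the AFT fit. The ratio of the standard error with severity to that without was 1.01, 0.97, 0.91 and 0.85 at R² = 0, 0.10, 0.20 and 0.30, close to the formula. At 90 subjects only R² = 0 was simulated (1.01); the other figures for 90 come from the formula.

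**Cox fallback, same simulation, R² = 0.30.** The mean log hazard ratio moved from 0.405 to 0.548, its standard error rose from 0.296 to 0.325, and the nominal 5% rejection rate rose from 0.26 to 0.45. The adjusted model estimates a less attenuated effect; its interval is not narrower. Some fits gave convergence warnings, so these figures are indicative.

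**Chance imbalance.** Assume 30% to 50% of subjects are on oxygen at baseline and use a normal approximation. The SD of the difference between arms is √(p(1 − p)(1/n₁ + 1/n₂)): 0.102 to 0.112 for 60:30, and 0.125 to 0.137 for 40:20. The probability of a difference above 15 percentage points in either direction is then about 14% to 18% for 60:30 and 23% to 27% for 40:20.

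**Zero times.** SAP 3.1.1 writes + 1 for study day and SAP 4.5 writes it for ICU stay; SAP 4.2.9 gives no formula. The protocol's after-discharge schedule starts on the study day following discharge, and its first column includes Day 2, so discharge on Day 1 is foreseen. Its frequency is not given.

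**The case against.** **This is a preference about efficiency, not an error.** That stands. Adjusting for the stratification factor is valid, and the SAP departs from nothing in the protocol. A reader might infer that the age-only model biases the comparison. The documents do not support that: the arms are randomized, and severity can differ between them only by chance. Baseline NEWS, oxygen saturation and supplemental oxygen are tabulated by arm (SAP 4.1.2), so an imbalance would be seen, though not adjusted for.

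**The size is assumed.** That stands too. It is tempting to call severity the main driver of length of stay, but no passage says so, and R² could be near 0. Even at R² = 0.30 the 60:30 interval factor falls only from 1.36 to 1.29.

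**NEWS was left out of the respiratory model on purpose.** NEWS scores respiration rate, oxygen saturation and supplemental oxygen (SAP Table 9), which overlap with that endpoint. This may be the reason, but the SAP does not give it, and overlap does not bar a baseline covariate. NEWS also covers all five components of the vital-signs endpoint and is a covariate there, and the Day 8 model adjusts for baseline category on the same scale. What does stand is that subjects already normal at entry are censored then, which narrows the range of severity. The gain may therefore be smaller than for discharge.

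**Borrowing the Day 8 rule would backfire.** Correct. If that model does not fit, SAP 4.2.1 deletes age category first, which is the stratification factor. The usual-activity model has no rule for merging ordinal levels. The ICU level may be sparse, since subjects must be able to swallow tablets and capsules (Protocol 4.1).

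**Zero times.** A reader might infer that the fastest discharges vanish from the analysis. They would be lost only from the log-time AFT fit; Kaplan-Meier, logrank, Gehan-Wilcoxon and Cox can use a time of 0. With no formula stated, this is a request for clarification.

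**Conclusion.** The point holds as an avoidable loss of efficiency in two secondary, estimation-only analyses. The text is clear: both models adjust for age category without a severity covariate, no reason is given, and a suitable covariate is already in use elsewhere in the SAP.

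The consequence is conditional. The AFT interval on the log scale would be about 5%, 11% or 16% narrower if severity explained 10%, 20% or 30% of residual log-time variance, and about 1% wider if it explained none. These R² values are assumptions, and narrower intervals apply to the AFT analysis only. In the Cox fallback the benefit is less attenuation and more power. The case is firmer for discharge than for respiratory improvement. The zero-time matter is a secondary clarification of unknown frequency. Neither affects the primary pharmacokinetic objective.

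**What to change.** 1. **SAP 4.2.9:** prespecify the baseline ordinal category (ICU, ward with oxygen, ward without oxygen), in addition to age category, as a covariate in the AFT model for time to discharge and in its Cox fallback.
2. **SAP 4.2.1, respiratory status:** do the same, leaving NEWS out if the sponsor wishes, and note that the gain may be smaller here.
3. **Fallback for both:** if a level is sparse or the model does not fit, merge or drop the ordinal category and keep age category. Do not copy the deletion order of the Day 8 model.
4. **SAP 4.2.9:** state that time to discharge = discharge date − date of first intake + 1, as is done for study day and ICU stay.

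The cost is a few lines of SAP text before unblinding and one or two extra model parameters, worth about 1% in standard error if severity is not prognostic. The + 1 lengthens every discharge time by a day, so the time ratio should be reported on that scale. No new data are needed, and the protocol names no covariates for discharge that this would contradict.

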4.3.2. Clinical laboratory tests

Laboratory parameters of hematology, serum chemistry and urinalysis will be investigated: All analyses will be done on SI-converted values as available in the database.

In case a laboratory test result is *censored* (no numeric value is available, but only a verbatim term), the following rules are applied:

- ‘<x’ or ‘>x’: a numeric value will be imputed by a value exceeding the cut-off value with one unit
- ‘≤x’ or ‘≥x’: imputation by x.

The laboratory abnormalities will be determined according to the criteria specified in the WHO grading table (see Appendix 2), available toxicity grades in the laboratory raw data will not be used. In case no toxicity grades are defined for a test, the abnormalities (above/below normal range) will be used. In determining toxicity grades/abnormalities the following rules are applied:

- Worst grades/abnormalities are determined over the whole observational period for each trial phase separately, including all post-reference scheduled and unscheduled measurements of that phase.
- The abnormalities “abnormally low” and “abnormally high” are considered equally important, i.e. if a subject has as well an abnormally low as an abnormally high value post-reference, both abnormalities are shown in the tables. (This means that the sum of the percentages can be more than 100%)
- If, for a specific test, the grading list provides distinct limits for abnormally low (=hypo) values as well as for abnormally high (=hyper) values, this test should be repeated for hyper and hypo limits separately in cross-tabulations.

Actual values and change from baseline will be summarized by treatment group at each scheduled time point.

An abnormality (toxicity grade or abnormality based on normal ranges) will be considered treatment-emergent in a particular phase if it is worse than the reference corresponding to this phase. If the reference is missing, the abnormality is always considered as treatment-emergent. A shift from “abnormally low” at reference to “abnormally high” post reference (or vice versa) is also treatment-emergent. The treatment emergent definition is applicable in both, the treatment and follow-up phase.

The number and percentage of subjects will be shown in a cross-tabulation of the toxicity/abnormality post-baseline versus baseline at each scheduled time point.

Additionally, a cross-tabulation of the worst toxicity/abnormality versus baseline will be presented per phase (Treatment phase, Follow-up phase) and for the combination of Treatment and follow-up phase. This table will also show the number and percentage of subjects per worst toxicity/abnormality, the number and percentage of subjects per treatment-emergent worst toxicity/abnormality, and the cumulative number of subjects per treatment-emergent toxicity/abnormality or worse.

Mean \pm SE graphs over time for the actual values and changes from reference will be generated for all tests performed.

A listing of abnormal individual subject hematology and clinical chemistry values from scheduled and unscheduled time points will be provided. This listing will include all other time points for the corresponding subject/parameter.

Grade 2 or higher toxicity laboratory values will be listed separately.

Urinalysis results will be listed. Proteinuria and urine WBCs will be summarized.

4.3.3. *Electrocardiograms*

PR duration, QT duration, QRS duration, Heart Rate and QTc intervals using Bazett’s correction formula and Fridericia’s correction formula will be investigated. QTc values will be used as reported, they will not be recalculated.

The actual values of QT/QTc will be categorized into abnormalities using the boundaries defined in the table below:

Abnormality codes:	QT/QTcorrected
“Normal”	≤ 450 ms
“]450 ms, 480 ms]”	$450 \text{ ms} < \text{QTc} \leq 480$ ms
“]480 ms, 500 ms]”	$480 \text{ ms} < \text{QTc} \leq 500$ ms
“More than 500 ms”	$\text{QTc} > 500$ ms

Abnormalities on the change from reference will be defined for QT/QTc, as follows

- < 30 ms (Normal)
- $[30; 60]$ ms
- > 60 ms.

Only increases by ≥ 30 ms will be considered as abnormalities. (Note: the QTc definitions for abnormalities follow the ICH E14 guidance.)

Worst abnormalities are determined over the whole observational period for each trial phase separately, including all post-reference scheduled and unscheduled measurements of that phase.

An abnormality will be considered treatment-emergent in a particular phase if it is worse than the reference corresponding to this phase. If the reference is missing, the abnormality is always considered as treatment-emergent. Abnormalities on changes from reference are always defined as treatment-emergent.

Actual values and change from baseline will be summarized by treatment group at each scheduled time point.

The number and percentage of subjects will be shown in a cross-tabulation of the toxicity/abnormality post-baseline versus baseline at each scheduled time point.

Additionally, a cross-tabulation of the worst toxicity/abnormality versus baseline will be presented per phase (Treatment phase, Follow-up phase) and for the combination of Treatment and follow-up phase. This table will also show the number and percentage of subjects per worst toxicity/abnormality, the number and percentage of subjects per treatment-emergent worst toxicity/abnormality, and the cumulative number of subjects per treatment-emergent toxicity/abnormality or worse.

Mean \pm SE graphs over time for the actual values and changes from reference will be generated for all tests performed.

A tabulation of the worst QT/QTc change versus baseline per treatment per phase will be presented.

Abnormal individual subject ECG values or abnormalities on the changes will be listed.

4.3.4. *Vital Signs*

Systolic and Diastolic blood pressure, oral temperature, pulse rate, respiratory rate, arterial oxygen saturation and level of consciousness will be investigated.

Vital Signs abnormalities will be determined according to the WHO grading scale and the boundaries defined in Appendix 3.

Worst toxicities are determined over the whole observational period for each trial phase separately, including all post-reference scheduled and unscheduled measurements of that phase.

Actual values and change from baseline will be summarized by treatment group at each scheduled time point. A toxicity will be considered treatment-emergent in a particular phase if it is worse than the reference corresponding to this phase. If the reference is missing, the abnormality is always considered as treatment-emergent.

The number and percentage of subjects will be shown in a cross-tabulation of the toxicity/abnormality post-baseline versus baseline at each scheduled time point.

Additionally, a cross-tabulation of the worst toxicity/abnormality versus baseline will be presented per phase (Treatment phase, Follow-up phase) and for the combination of Treatment and follow-up phase. This table will also show the number and percentage of subjects per worst toxicity/abnormality, the number and percentage of subjects per treatment-emergent worst toxicity/abnormality, and the

63623872FLZ2002 Statistical Analysis Plan

cumulative number of subjects per treatment-emergent toxicity/abnormality or worse.

Mean \pm SE graphs over time for the actual values and changes from reference will be generated for all tests performed.

A listing of abnormal individual subject VS values will be provided.

